After completing training, each counsellor will be assigned to 5 pregnant women who consent to receiving breastfeeding counselling. Two counselling sessions will be scheduled prior to delivery, and then peer counsellors will visit mothers post-delivery in their homes. Research staff will also visit mothers to collect data on breastfeeding practices and to obtain feedback on the benefit of BEST4Baby and mHealth tools used during the course of the project. A comparison group of mothers will be utilized to evaluate the influence of peer counselling on breastfeeding practices.

Project Narrative

Breastfeeding is good for mothers, good for babies and an especially cost-effective means for promoting infant survival, healthy growth and development. Yet a very large portion of the world's infants, including those in India, lack the benefit of optimal breastfeeding practices.

Breastfeeding Support Tool for Baby (BEST4Baby) will utilize exploratory research and community involvement to design and integrate mobile technology, culturally-appropriate breastfeeding education, and a community-based approach to increase breastfeeding support to mothers; and the initiative will provide evidence that the BEST4Baby approach can achieve the public health objective of improving rates of exclusive breastfeeding for 6 months and continued breastfeeding for an appropriate time thereafter.

Background

Breastfeeding (BF) reduces morbidity and mortality during the first year of life and decreases the incidence of mal-nutrition, acute and chronic infections, allergy, childhood cancers, childhood-onset diabetes and childhood obesity¹⁻³. Breastfeeding also protects against infant mortality, especially during the first six months of life¹⁻³ and has short-term and long-term effects yielding health benefits which could prevent 13% of all deaths in children under five⁴. The effect of natural feeding in reducing infant mortality is significant^{3,5} and has the potential to reduce as many as 156,000 child deaths each year in India and prevent 3.4M respiratory infections, and 3.9M episodes of diarrhea in young children. Global rates of optimal BF practices, especially exclusive breastfeeding (EBF), have remained stagnant over the past decade both in India and in a number of under-resourced countries^{6,7}.

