Multimedia content. Multimedia content will be developed based on Social Cognitive Theory (SCT)³⁹, Theory of Planned Behavior (TPB)⁴⁰ and social marketing (e.g., health branding) approaches^{41,42} for use by peer counselors for breastfeed during the home visits. Message development will follow active audience engagement methods and be suitable for use by peer counselors to provide information to mothers during antepartum home visits.

Communication features. Timely communication of information based around post-partum time sequence and baby's milestones will be developed to assist the peer counselors in promoting optimal breastfeeding practices. Counselors may be reminded of the need for follow-up via text reminders and communications may support the home visits by providing helpful hints that are introduced in a timely manner. For example, the peer counselors could be prompted to discuss the topic of EBF at 28 weeks GA and at a second visit 1-2 weeks before anticipated delivery.

Months 15-23

For Specific Aim 2, we will pilot test the BEST4Baby program in a real-life setting within the 6 clusters of the larger Global Network research area located in Belagavi District (Karnataka, India). The pilot study will evaluate training for 24 peer counselors recruited from study areas and providing consent; and the study will assess use of the BEST4Baby program to support counselors as well as mothers recruited and consented by research staff to receive peer counseling. Each peer counselor will counsel 5 mothers to achieve a sample adequate to establish an effect size.

Peer Counselors for Breastfeeding Support. The 24 peer counselors will evaluate the usability and acceptability of the mHealth app for the training and support provided. We will perform pre- and post-tests to identify knowledge acquired as a result of peer counselor training and administer a post-training survey on the usability and acceptability of the BEST4Baby program. As peer counselors are being trained, they will receive an ID badge²⁸, the BEST4Baby mobile application and branded BEST4Baby mobile device to support the training.

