Subjects that take the BEST4Baby training will take pre- and post-tests to assess if training increased breastfeeding knowledge; these women will also be asked to provide feedback relative to the acceptability of mHealth technologies and tools developed during the BEST4Baby program and to share perceptions about the perceived feasibility of continuing their use during an extended period of service as a counselor. Mothers will be recruited by research staff and asked to consent to being counseled during home visits and to providing data needed for purposes of BEST4Baby. Research staff will obtain feedback and ask questions to generate information about breastfeeding (e.g., when it was initiated, if exclusive breastfeeding occurred, how long any type of breastfeeding was maintained, and intent to continue breastfeeding beyond the close of BEST4Baby). A group of mothers not receiving peer counseling will also consent and serve as a comparative group to assess if breastfeeding practices are better among peer-counselled mothers compared to mothers not having peer counseling.

It is planned that data generated by the BEST4Baby formative research will be utilized for the design of a clinical trial that can generate definitive findings relative to the effectiveness of mobile technologies to promote optimal breastfeeding and to increase sustainability of a peer counselor model for delivery of breastfeeding support.

Describe the characteristics of the subject population, including their anticipated number, age range, and health status, if relevant. Focus groups will have 8-10 participants and all participants will consent before initiation of focus group discussions. At least two focus groups will be held for each target group described below, except that there will be at least one Target Group A focus group in each of the six clusters selected from among the clusters located within the larger JN Medical College Global Network study area for participation in BEST4Baby. Characteristics of focus group target groups follow.

Target Group A: This group will be comprised of mothers who have breastfed at least one child in the past three years. Other inclusion criteria include: 18 years of age, and willing to provide informed consent. To the extent feasible, mothers representing the diversity that exists in the cluster of residence will be encouraged to participate. A Target Group A focus group will be held in each of the 6 clusters participating in BEST4Baby.

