The mothers who will be recruited to receive breastfeeding counseling and support will be women living in study clusters who are in their third trimester of pregnancy and who consent to interaction with the breastfeeding counselor who will contact them prior to delivery and then make home visits for breastfeeding counseling according to an agreed upon schedule and consistent with the BEST4Baby protocol. Peer counselors will be expected to counsel 5 mothers during an approximately 9-month pilot-testing phase. Thus, with 24 counselors, 120 mothers will be counseled. Additionally, 120 mothers from clusters that are not participating in BEST4Baby and not receiving counseling through BEST4Baby will be consented and serve as a comparison group to allow assessment of the influence of peer counseling on breastfeeding practices and intent to continue breastfeeding for the recommended period of time.

Describe and justify the sampling plan, including retention strategies and the criteria for inclusion or exclusion of any subpopulation. Due to the exploratory nature of the proposed research, there is no rigid sampling plan. Field research staff assigned to recruit subjects for focus groups will be presented criteria for including subjects that have characteristics of the target groups specified above. At the same time, staff will recruit participants that are reasonably representative of the diversity that may characterize a cluster.

Some individuals to be interviewed may be interviewed at location at which they can be found, and which will accommodate a private interview. For example, we anticipate interviewing fathers at a delivery facility they may be visiting prior to discharge of mother and baby. Government officials will be selected due to the need to collect information useful due to their role related to breastfeeding rather than personal characteristics.

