It is desirable to involve subjects of diverse socio-economic status in BEST4Baby, including those that may be of lower socio-economic status. Modest compensation based on consideration of time or costs associated with participation in the project will be provided to subjects participating in focus groups or as breastfeeding counselors; however, the compensation will not be substantial enough to represent a means of pressuring lower income subjects to participate.

If relevant to the proposed research, describe procedures for assignment to a study group. As related to human subjects protection, provide details about all planned interventions such as dose, frequency, and administration. BEST4Baby encompasses exploratory research; thus subjects are not randomly assigned to an intervention or control group. Rather, those that reside in a study cluster or work with a facility serving such a cluster (in the case of a Target Group C) and have characteristics appropriate for a focus group, interview, counselor education and training, or breastfeeding counseling and support will have the opportunity to participate if willing to consent to participation. Mothers (12) who reside in adjacent communities outside of the six BEST4Baby study clusters and not provided breastfeeding counseling will be asked to consent to serve as a comparison group to the 120 mothers counseled to enable effect size of the influence of peer counseling on breastfeeding practices.

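### No rule says which consenting women fill the counselled or comparison places, and the two groups agree to very different commitments, so the Objective 2.2 effect size may include volunteer selection of unknown size

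*Combined protocol and SAP*

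**What the plan says.** **Counselled mothers.** Section I.a describes them as "women living in study clusters who are in their third trimester of pregnancy and who consent to interaction with the breastfeeding counselor". The Project Summary says that "each counsellor will be assigned to 5 pregnant women who consent to receiving breastfeeding counselling". Recruitment is by research staff, not by the counsellors (Section I.a: "Mothers will be recruited by research staff and asked to consent to being counseled during home visits"; the Months 15-23 text likewise refers to "mothers recruited and consented by research staff to receive peer counseling"). The Intervention and Data Collection Plan sets a minimum of nine counsellor visits, and the retention text in Section I.a makes willingness to stay engaged for longer a requirement of pilot recruitment.

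**Choice among eligible women.** The sampling answer in Section I.a says "Due to the exploratory nature of the proposed research, there is no rigid sampling plan". It then turns to focus groups ("Field research staff assigned to recruit subjects for focus groups will be presented criteria for including subjects that have characteristics of the target groups") and adds that "staff will recruit participants that are reasonably representative of the diversity that may characterize a cluster". The assignment answer in Section I.a says that those with suitable characteristics "will have the opportunity to participate if willing to consent to participation". Section IV.a foresees information meetings and community outreach as ways to find participants.

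**Comparison mothers.** The Comparison Cohort paragraph describes 120 women who deliver in facilities, live far enough away to avoid contamination, give consent, and answer a simple survey at baseline and six months. No sampling rule is given for them either.

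**Analysis and use.** The groups are not randomised. The Month 24 Data Analysis text plans bivariate tests and exact logistic models on a dosage index. No between-group estimate adjusted for baseline differences is specified. The comparison cohort is there to allow effect and sample size calculations, and the findings are to support an application for a fully powered trial. Section II lists survey items on breastfeeding knowledge, attitudes and intentions, without their timing or any use as covariates.

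**The concern.** A woman who agrees to two prenatal sessions and repeated home visits about breastfeeding may already intend to breastfeed more firmly than one who agrees to two surveys. If so, the counselled group is partly selected on a cause of the outcome, and the comparison group less so. Recruitment through meetings, where interested women come forward, could add to this. The crude difference would then mix programme effect with volunteering.

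The difference is the product of Objective 2.2 and is meant to size the next trial. An inflated value would leave that trial too small. The plan also foresees no count of women eligible, approached or refusing; retention is followed only from consent. The extent of selection could therefore not be judged afterwards.

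**Working it through.** **1. The plan's own figure.** 6 clusters × 4 counsellors = 24; 24 × 5 = 120 counselled mothers, or 20 per cluster. This reproduces. The plan gives no alpha, power, target effect or dropout, so there is no power-based sample size to check.

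**2. The two groups side by side.**

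| | Counselled | Comparison |
|---|---|---|
| Consent | yes | yes |
| What is accepted | at least 9 visits, plus data collection | baseline and six-month survey |
| Stated conditions | study cluster, third trimester | facility delivery, suitable distance |
| Rule for choosing among eligible women | none | none |
| Count of eligible or refusing women | none | none |

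**3. Illustration of size (no programme effect).** Let s_C and s_K be the motivated shares in the counselled and comparison groups, and p_m and p_u the exclusive breastfeeding rates in motivated and other women. Then

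apparent difference = (s_C − s_K) × (p_m − p_u),

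with p_m and p_u fixed by the odds ratio and by s_K·p_m + (1 − s_K)·p_u = 0.20. The 20% is the six-month figure in the Significance section, whose wording is loose as to exclusive or any breastfeeding. The shares and odds ratios are assumptions.

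For s_C = 0.70 and s_K = 0.50:

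- Odds ratio 2: p_m = 0.254, p_u = 0.146; 0.20 × 0.108 = 0.022, or +2.2 points.
- Odds ratio 3: p_m = 0.283, p_u = 0.117; 0.20 × 0.166 = 0.033, or +3.3 points.
- Odds ratio 5: p_m = 0.316, p_u = 0.084; 0.20 × 0.232 = 0.046, or +4.6 points.

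More extreme assumptions give more: 90% against 50% gives +4.3 to +9.2 points, and 90% against 30% gives +7.1 to +16.8. Equal shares give 0. If the comparison group were the more motivated one, the sign would reverse.

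**4. Against the pilot's precision.** With 120 per group, two-sided 5% and no allowance for clustering, the difference detectable with 80% power from 20% is about 16 points. A spurious 2.2 to 4.6 points would give a significant result favouring counselling about 6% to 14% of the time. The main harm is therefore to the estimate rather than to the test.

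**5. Effect on the next trial.** Using n per arm = [1.96·√(2p̄q̄) + 0.842·√(p₁q₁ + p₂q₂)]² / (p₁ − p₂)², where p̄ is the mean of the two rates, with 80% power, two-sided 5% and individual observations (all assumed):

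- True 20% against 35%: 138 per arm.
- If the pilot shows 40% because of 5 points of selection: 82 per arm.
- Power of 82 per arm for the true 15-point gain: about 58%.

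**The case against.** The case on the other side has real weight.

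- **The sampling sentence.** A reader might take it as describing how pilot mothers are chosen. It answers a heading about the whole study, but what follows concerns focus groups and interviews. It cannot carry the point alone. The point rests on the pilot text itself, which sets eligibility and consent and stops there.
- **Selection is not wide open.** Residence, trimester and adult age are set, research staff recruit, and an aim of reasonable diversity is written down. This stands, but none of it bears on intention to breastfeed. The eligible pool per cluster is not given; if it is near 20, staff have little choice to exercise.
- **Comparison mothers are filtered too.** A reader might infer that only the counselled group consists of volunteers. The documents do not support that: comparison mothers also consent, and facility delivery is an extra condition whose effect on the bias is unknown. What differs is the weight of the commitment.
- **Willingness may not track intention.** Women who expect difficulty may want counselling most. The documents do not settle this, so the net bias could run either way.
- **The pilot is openly exploratory.** It is non-randomised, treats exclusive breastfeeding as a secondary outcome and leaves definitive evidence to a later trial. That excuses the lack of randomisation. It does not excuse an unrecorded selection process behind a number used to size that trial.

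**Conclusion.** The point holds in limited form. Neither group has a rule for choosing among eligible women, the commitments differ sharply, and no baseline-adjusted group comparison is specified. The effect size may therefore include differential volunteer selection. Inflation is plausible; its direction is not established and its size is unknown.

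A reader might infer that the effect size is certainly inflated, or by a large amount. Larger figures need either very unequal motivated shares or the assumption that women are selected directly on the outcome, with no selection in the comparison group. The documents contain no refusal, pool-size or motivation data to support either. The +2 to +5 points rests on assumed shares of 70% and 50%, an odds ratio of 2 to 5, and a 20% comparison rate. It shows what a moderate imbalance would do and is not an estimate for this pilot.

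**What to change.** Before pilot enrolment:

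1. **Same approach rule in both groups.** List eligible third-trimester women by expected delivery date, by counsellor area in the study clusters and by community for the comparison group. Approach them in list order until the places are filled. State how the facility-delivery condition fits a list drawn up before delivery.
2. **Participation log in both groups.** Record women eligible, approached, consenting and refusing, with age, parity and reason. Report participation rates beside the effect size.
3. **Intention before counselling.** Take the intention items already planned in Section II before any counselling, at the same stage of pregnancy in both groups.
4. **Adjusted estimate.** Prespecify a between-group effect size adjusted for baseline intention, reported next to the crude one on the same scale.
5. **Stated limit.** Say that list order removes recruiter discretion and reliance on women coming forward, but not refusal of the nine-visit commitment. Residual volunteer bias must be acknowledged when the effect size is used to plan the next trial.

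The cost is a listing step and a log for existing recruiters, and slightly less freedom to match mothers with nearby counsellors. Comparison mothers would need a contact before delivery if their baseline survey is not already planned then. The 120 per group and the counselling itself are unchanged.
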